7.2.5. Pruritus assessed by numerical rating scale and disability

Assessments of pruritus such as duration (hours per day), Numerical Rating Scale (NRS) score and disability will be presented primarily at each visit using wound level listings. A table will be provided for summary statistics of NRS score by visit at wound level. Additional descriptive summary table will be provided for NRS score by visit regardless of body region and subject. Another table will report count and percentages of disability by visits at wound level as well.

7.2.6. Surgeon's assessment of BTM application

Surgeon's assessment of BTM application such as BTM is easy to use, BTM is easy to apply, BTM is easy to delaminate, BTM is a product I would use for burn patients and total scores will be presented primarily at each visit using wound level listings. The result of surgeon's assessment of BTM application will be summarized by site regardless of wound level and subject.

8. Safety Analysis

Specific assessments to evaluate treatment device safety include the following: the frequency and type of adverse events, clinically significant laboratory abnormality, and vital signs. All analyses of safety will be conducted using the ITT population.

8.1. Adverse Events

An AE can be any unfavorable and unintended sign (including an abnormal laboratory finding, for example), symptom, or disease temporally associated with the use of an investigational product, whether or not considered related to the product. All AEs encountered during the study will be reported in detail in the CRF, starting at the time of the first screening/eligibility assessment and ending at the end of the study for each subject. Pre-existing conditions that worsen during a study are to be reported as AEs. Clinically significant changes in physical examination, standard of care laboratory safety tests, and vital signs will also be defined as AEs and recorded appropriately. All AEs will be coded using the MedDRA Dictionary (MedDRA, Version 18.1 or higher).

A study-specific subset of AE events called Unanticipated Adverse Device Effect (UADE) will be introduced to the safety analysis of this study. UADE is defined as “any serious adverse effect on health or safety or any life-threatening problem or death caused by, or associated with, a device, if that effect, problem, or death, was not previously identified in a nature, severity, or degree of incidence in the investigational plan or application (including a supplementary plan or application), or any other unanticipated serious problem associated with a device that relates to the rights, safety, or welfare of subjects” (21 CFR 812.3). The UADE will be identified by the Principal Investigator (PI) on site and reported in the CRFs.

Imputation for missing AE onset dates can be found in Appendix 13.3.

An overview summary of the number and percentage of subjects with any AE, SAE, AE related to study device, AE leading to early termination, and AE leading to death will be provided with ITT population. A repeated analysis will be conducted for the subset of UADEs.

8.1.1. Incidence of Adverse Events

Summaries of the total number of AEs and the number and percentage of subjects with at least one AE will be provided for the ITT population by system organ class (SOC) and preferred term (PT). At each level of subject summarization, a subject is counted once if the subject reported more than one event. A repeated analysis will be conducted for the subset of UADEs.

All AEs will be presented in a listing for the screening population.

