## PROTOCOL SYNOPSIS

Study Title	A Traditional Feasibility Study to Assess the Safety and Effectiveness of the Biodegradable Temporizing Matrix (BTM) in the Treatment of Deep Burn Skin Injuries.
Protocol Number	CP-002
Study Population	Up to 15 subjects, male and female adults ( $\geq 18$ years and $\leq 70$ years) who have sustained deep dermal/full-thickness burn injuries between 10% and 70% of Total Body Surface Area (TBSA), will be enrolled to ensure 10 subjects are available for evaluation at the 3-month post Split-Skin Graft assessment.
Study Sites	Up to 6 US sites may participate in the study.
Study Duration	Approximately 20 months (includes 3 months startup and 3 months enrollment)
Estimated Time to Complete Enrollment	6 months
Subject Participation Duration	
Subjects will be on study for approximately 14 months
 
Screening: approximately 1-2 days
 
Treatment: approximately 2 months (from admission to hospital through to the end of graft 'take' (remains viable))
 
Follow-up: 12 months

Description of Device	The Biodegradable Temporizing Matrix (BTM) comprises a completely synthetic, sterile, integrating dermal component (porous biodegradable polyurethane foam) and a temporary epidermal barrier component (a non-biodegradable polyurethane sealing membrane). These layers are adhered with a biodegradable polyurethane bonding layer.

Description of Study Design	
This is a multi-center, single arm, traditional feasibility study to allow a preliminary assessment of the safety and effectiveness of BTM treatment. Patients with 10-70% TBSA of sustained burns will have BTM devices implanted in areas with deep partial or full thickness burns. At least 5% and a maximum of 50% TBSA of the sustained burns will be treated.

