## 3 STUDY DESIGN

### 3.1 Study Population

The study population includes severely ill subjects who have sustained life threatening deep burn injuries and who would usually receive Integra® dermal regeneration template, a similar dermal matrix, xenograft or cadaver allograft, to facilitate functional healing (i.e. those subjects with >10% TBSA full thickness burn injuries). However, beyond the upper end of this range (>70% TBSA full thickness burns), subjects with such injuries experience high subject mortality so that their inclusion in such a trial is not deemed prudent. Instead, this trial aims to recruit a minimum of ten subjects and a maximum of up to 15 subjects suffering deep-dermal or full thickness burn injuries to between 10% and 70% TBSA and who are able to provide informed consent, or have a legal representative who is able to make medical decisions on behalf of the subject.

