#### **4.5.2 Handling of Subject Withdrawals or Subject Discontinuation of the Investigational Device**

Subjects withdrawn early due to an AE will be followed until medically stable or resolution of the AE.

If withdrawal from the study is requested by the subject, prior to BTM integration (i.e. **before Day 7** post-implantation), the BTM device can be removed and the wound bed closed by the application of an autologous SSG. However, **≥ Day 7** the BTM can be removed, but it is **not recommended**, as integration will likely have occurred to a point such that BTM removal would result in damage to the subject's burn wound. In either case, no data or BTM -related follow-up will be imposed. Physicians are expected to follow subjects according to their institution's standard of care. Investigational Device Exemption (IDE) regulations require investigators to maintain each subject's case history and exposure to the device.

All consented subjects who have been implanted with BTM, even in the event of device failure, will have all lesions followed up as a part of the study until completion or if/when withdrawal from the study is requested by the subject.

If subjects do not complete 3 months follow up **post SSG** implantation for any reason, they will be replaced with further subjects that meet the inclusion/exclusion criteria, to

ensure that the final cohort is (a minimum of) 10 subjects.

In case of withdrawal, the Investigator will promptly inform the Institutional Review Board (IRB) within 5 working days and will provide the reason(s) for the withdrawal. All applicable source documentation will be collected to confirm resolution.

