2.4. Study Endpoints

2.4.1. Primary Endpoint

- Incidence and type of adverse events occurring after BTM implantation. These data will be reviewed by a Data Safety Monitoring Board (DSMB).
- BTM 'take' rate: amount of BTM that has adhered to the wound bed at the time of skin grafting, expressed as a percentage of the total amount of BTM applied.
- SSG 'take' rate over BTM: applied skin graft which 'takes' expressed as a percentage of the total amount of BTM-treated SSG applied 7 -10 days after application of the SSG.

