2.5. Treatments

The BTM is designed to be implanted into a newly debrided wound bed and stapled or sutured to the edge of the wound. The BTM provides a scaffold to facilitate dermal repair whilst keeping the wound physiologically ‘closed to reduce wound contraction’. When integration is complete, typically within 28 to 35 days, the combined bonding layer and sealing membrane is peeled off, or can be left in place longer (>30 days) if more time is required for donor skin graft preparation, and discarded leaving only the implanted foam layer to biodegrade.

The BTM device is not intended to be used on the hands, face, neck, plantar skin, or perineal area.

3. General Statistical Considerations

Continuous variables will be summarized using the appropriate descriptive statistics: number of observations (n), mean, standard deviation (SD), median, minimum, and maximum. Categorical variables will be summarized using the frequency and percentage of observed data. All tabulated data will be presented in subject level listings as source data. In general, no formal inferential statistics are to be performed due to the small sample size unless specified otherwise in the statistical analysis plan.

For the summary statistics of all numerical variables unless otherwise specified, minimum and maximum will be displayed to the same level of precision as reported. Mean and median will be displayed to one level of precision greater than the data collected. The standard deviation or standard error will be displayed to two levels of precision greater than the data collected.

Due to the small sample sizes, all p-values derived from inferential analyses will be considered informative. In general, all significant testing will be two-sided at significance level 0.05. All tests will be made without adjustment for multiplicity or multiple comparisons. P-values will be rounded to four decimal places. If a p-value is less than 0.0001 it will be reported as "<0.0001". If a p-value is greater than 0.9999 it will be reported as ">0.9999".

When frequencies are presented, the percentage will be suppressed when the count is zero in order to draw attention to the non-zero counts. A row denoted "Missing" will be included in count tabulations where necessary to account for dropouts or missing data. The denominator for all percentages will be the number of subjects within the analysis population of interest, unless otherwise specified.

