3.3.2. ITT Population

The Intent-to-Treat (ITT) Population consists of all subjects treated with a BTM. All safety and efficacy analyses will be performed using the ITT population.

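### Adverse event incidence uses all treated subjects as denominator at every stage, so late first-onset events are understated if subjects withdraw or are lost early

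*SAP*

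**What the plan says.** The first primary endpoint is "Incidence and type of adverse events occurring after BTM implantation" (SAP 2.4.1), with no time horizon. SAP 8.1.1 gives, by system organ class and preferred term, the total number of AEs and "the number and percentage of subjects with at least one AE will be provided for the ITT population". The overview in SAP 8.1 and the tables in 8.1.2 to 8.1.4 (relationship, grade, serious events) count subjects in the same way.

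The denominator follows from two rules. SAP Section 3 states: "The denominator for all percentages will be the number of subjects within the analysis population of interest, unless otherwise specified". SAP 3.3.2 says that the ITT population "consists of all subjects treated with a BTM. All safety and efficacy analyses will be performed using the ITT population". The AE sections specify no other denominator.

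On early leavers, Protocol 4.5.2 says of subjects who do not complete 3 months after SSG that "they will be replaced with further subjects that meet the inclusion/exclusion criteria". Protocol 3.1 gives the range as "a minimum of ten subjects and a maximum of up to 15 subjects", and the Protocol Synopsis explains that up to 15 "will be enrolled to ensure 10 subjects are available for evaluation at the 3-month post Split-Skin Graft assessment". Protocol 8.2 ends recording 7 days (AEs) or 30 days (serious AEs) after a subject's last day in the trial. Protocol 4.5.2 imposes no further follow-up after a withdrawal that the subject requests.

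Neither document plans an AE table by period, with numbers at risk, or with person-time. The SAP does plan a listing of all AEs (8.1.1) and a table of early discontinuations with reasons (4.1).

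**The concern.** A subject who leaves at, say, one month cannot be seen to have a first event at eight months. In the planned table that subject still adds one to the denominator and nothing to the numerator of every row in which no earlier event was recorded. For late events the percentage therefore falls as early withdrawal rises, whatever the device does, and the error favours the device.

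Late events are a real part of the safety question. The foam layer stays in the wound after the seal is removed (Protocol 5.1). In the free-flap pilot, microscopic remnants were still seen at 12 months (Protocol 1.2.2). Device-related events already reported in the burn pilot include graft breakdown (n = 2) and joint contracture (n = 3) (Protocol 1.2.2).

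The study tests no hypothesis (Protocol 11.1), so the descriptive percentages are its result. The Protocol Synopsis says that the safety and efficacy evaluations will guide the design of the pivotal trial.

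**Working it through.** The plan has no figure to reproduce: N = 10 was chosen without a calculation (SAP 3.1) and no drop-out rate is given. The check asks how far the planned percentage can move.

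**Inputs from the documents.** 10 subjects evaluable at 3 months after SSG; at most 15 enrolled, hence at most 5 early leavers; denominator = all treated.

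**Assumptions.** Late means first onset after 3 months post SSG (the documents do not define it). Every enrolled subject is treated. Exactly 10 subjects are under follow-up at 3 months. In steps 1 and 2 nobody is lost later and early leavers are alive.

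**Step 1: dilution factor.** With x subjects having a late event, the plan reports x/N and the at-risk percentage is x/10. Since x/N = (x/10) × (10/N), the factor is 10/N.

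| Early leavers | N treated | Factor 10/N | 3 late events reported as |
|---|---|---|---|
| 0 | 10 | 1.00 | 30.0% |
| 1 | 11 | 0.91 | 27.3% |
| 2 | 12 | 0.83 | 25.0% |
| 3 | 13 | 0.77 | 23.1% |
| 4 | 14 | 0.71 | 21.4% |
| 5 | 15 | 0.67 | 20.0% |

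**Step 2: uncertainty at the extreme.** The SAP plans no intervals; these only show scale. Exact 95% limits for three events are 6.7% to 65.2% with 3/10 and 4.3% to 48.1% with 3/15. With no late events, the one-sided 95% upper bound is 1 − 0.05^(1/10) = 25.9% for 0/10 and 1 − 0.05^(1/15) = 18.1% for 0/15.

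**Step 3: losses after month 3.** These are not replaced. With 15 treated and 1, 2 or 3 later losses, the factor for events at the end of follow-up is 9/15 = 0.60, 8/15 = 0.53 or 7/15 = 0.47.

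**Step 4: early deaths.** A subject who dies early can have no late event, so counting that subject in the denominator is right. Suppose k of the 5 early leavers died and the rest withdrew, and 3 of the 10 still followed have a late event. The cumulative incidence with death as a competing event is (1 − k/15) × 3/10 = 30%, 28%, 26%, 24%, 22%, 20% for k = 0 to 5. The planned table reports 20% throughout, which is exactly right when all five died.

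**The case against.** The strongest reply is that little may be lost in practice. Protocol 4.5.2 keeps all implanted subjects in follow-up, even after device failure, unless they ask to withdraw, and Protocol 4.3 requires contact at least monthly. If nobody leaves early, there is no early-leaver dilution. In severe burns some early exits may be deaths, which do not dilute. Many of the device events reported earlier (fluid or blood under the seal, delamination, integration failure) arise before or around grafting and would usually be observed. Joint contracture is also listed by visit (SAP 7.2.3), infections are summarised by visit (SAP 8.2), and with 10 to 15 subjects a careful reader could rebuild the numbers at risk from the listings. The intervals in step 2 overlap heavily, and no decision threshold depends on them.

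All of this stands, and it limits the scope and weight of the point. It does not correct the percentages that will be reported for the primary safety endpoint. The data safety monitoring board reviews do not correct them either.

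A reader might infer more than the documents support:

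- *That replacement causes the bias, or that replaced subjects should leave the denominator.* Replacement adds followed subjects and dilutes nothing. Removing early leavers from the ITT table would discard their early events.
- *That the whole primary safety endpoint is biased.* Only events first arising after a subject has left are affected, and only in rows where that subject had no earlier event.
- *That a 40% risk would be reported as 28%.* This follows from (10 × 0.40 + 5 × (1 − 0.6^(1/14)))/15 = 0.279. It needs a constant hazard, an assumed 40% risk over 14 months, and five leavers, all at one month and none by death. The same formula gives 36.7% with one leaver and 33.9% with two.
- *That SAP 6.2.1 rules out follow-up-adjusted rates.* Its heading ties that statement to time to delamination, which is a different matter from time under observation.

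**Conclusion.** The point holds in a limited form. If subjects withdraw or are lost, the planned percentages understate the incidence of late first-onset AEs among those who could be observed to have them. From leavers before 3 months alone, the relative reduction lies between none and one third (factor 1.00 to 0.67). Later losses add to it, and early deaths do not contribute. The range rests on 10 subjects remaining at 3 months and on the definition of late given above. Reading the at-risk percentage as an estimate for all treated subjects further assumes that those who left alive had the same late risk as those who stayed. The actual size depends on drop-out, which the documents do not predict. No test or threshold is affected. This is an inexpensive improvement to the reporting of a primary endpoint and does not undermine the study.

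**What to change.** Keep the crude ITT tables unchanged, so that early events in every treated subject are retained. Add to SAP 8.1.1, for all AEs, device-related AEs and serious AEs, a table of the number and percentage of subjects with an event starting in each phase:

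- implantation to final SSG;
- final SSG to 3 months;
- 3 to 12 months after final SSG.

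The denominator is the number under follow-up at the start of the phase. Using the final SSG as the boundary matches the schedule of assessments, which times follow-up visits from it when there are several grafts. Show subject-months of follow-up for each phase, so that losses within a phase are visible. A single rate pooled over 14 months would mislead if events cluster early. Report deaths in each phase separately, as competing events. State that late-event incidence will be interpreted from this table.

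Onset dates are already recorded (Protocol 8.1), and rules for incomplete dates are in SAP Appendix 12.3. The cost is a paragraph of SAP text and a few tables, with no change to conduct, sample size or burden on subjects. The drawbacks are slightly more output, small denominators, and late rates that may look less favourable.

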8.1.2. Relationship of Adverse Events to Study Device

The investigator will provide an assessment of the relationship of the event to the study device. The possible relationships defined in the protocol are “Not Related” and “Related”. The “Related” category will be further classified into possible, probable, and definite. The “Not related” category will be further classified into unlikely and not related.

The AEs categorized by SOC and PT will be summarized by relationship to study device in a manner similar to that described in Section 9.1.1 for the ITT population.

AEs that are missing a relationship will be presented in the summary table as “Related” but will be presented in the data listing with a missing relationship.

A repeated analysis will be conducted for the subset of UADEs.

8.1.3. Intensity Grade of Adverse Event

The NCI CTCAE (version 4.03 or higher) will be used for grading AEs.

The AEs categorized by SOC and PT will be summarized by intensity grade in a manner similar to that described in Section 9.1.1.

In the intensity grade table, if a subject reported multiple occurrences of the same SOC or PT, only the highest intensity grade will be counted. Missing intensity grade will be imputed as ‘Grade 3’ in tables but will be presented in the data listing with a missing severity.

A repeated analysis will be conducted for the subset of UADEs.

8.1.4. Serious Adverse Events

The seriousness of an AE should be assessed by the PI at site or PolyNovo (Sponsor) from the severity of the AE.

The SAEs will be categorized and presented by SOC and PT with overall population in a manner similar to that described in Section 9.1.1.

All SAEs will be presented in a listing as well.

A repeated analysis will be conducted for the subset of SAE UADEs.

8.1.5. Adverse Events Leading to Early Termination

It will be left to the Investigator’s clinical judgment to decide whether or not an AE is of sufficient severity to require the participant’s removal from treatment, prior to Day 7 after BTM implantation.

All AEs including UADEs leading subject to study discontinuation will be presented in a listing.

8.1.6. Death

All subjects who have an AE with an outcome of death will be presented in a listing.

8.2. The incidence and severity of infections at BTM-treated wound site

Assessments of the infections, such as severity, pattern, type or any other aspects of clinical interest will be presented primarily at each visit using wound level listing. The summary of infection incidents by visit and severity will be presented in a table. The number of wounds at each severity category including ‘having no infection’ will also be summarized by visit. Wounds with multiple infections will be counted once at the severity category determined by the highest level infection the wound has. For each subject, the ratio of the number of infected wounds to the total number of wounds will be calculated and a table summarizing those subject’s ratios using descriptive statistics will also be provided. Shift table from baseline to the worst post

baseline and from baseline to '7-10 days post SSG time point' in terms of severity will also be given at wound level respectively.

8.3. Clinical Laboratory Evaluations

There is no specific laboratory investigation for this traditional feasibility trial. All clinical laboratory evaluations will be managed by the site as per standard of care.

8.4. Vital Sign Measurements

Summary tables presenting observed values and changes from baseline will be provided overall for vital sign data, including systolic blood pressure (mmHg), diastolic blood pressure in mmHg, Heart rate in bpm, Respiratory rate in bpm, temperature in °C. A by visit summary table for vital sign using descriptive summary statistics will be provided. All vital sign data will be presented in a listing by subject and visit.

